
Though there are no known or anticipated drug interactions between losartan and ARVs, this has not been extensively studied. Therefore an intensive pharmacokinetics experiment will be conducted on all HIV infected subjects at month 1 of the study (when losartan is at steady state). In addition, levels of ARVs and losartan in plasma and PBMCs will be performed quarterly over the 30-month study period and intracellular levels of losartan and ARVs will be measured in LT at month 30. These analyses will be performed in semi real-time to ensure that subjects are not put at risk from unexpected drug-drug interactions.

We will enroll 5 HIV uninfected subjects who will not be randomized to a treatment arm and will not be given HPV vaccination. They will undergo a blood draw and inguinal LN biopsy at one time point only. We will enroll an additional 5 HIV uninfected subject who will not be randomized to a treatment arm nor given HPV vaccine. These 5 subjects will be given Stribild and Prezista for two weeks. In previous studies with HIV-positive individuals, we have shown lymph node concentrations of all ARVs to be suboptimal. No one has yet measured ARV concentrations in lymph nodes of healthy volunteers; we feel this is an excellent opportunity to answer that question. These subjects will return to the medical center for an inguinal LN biopsy and colonoscopy and blood draws at baseline, hours 1, 2, 3, 4, 6, 8, 12 and 24 at one time point only. The five control subjects who are taking Stribild and Prezista will be part of the MRI-sub-study (See Appendix I). This test will occur once during the two weeks while they are taking the antiretrovirals, prior to the biopsy.

In addition, these negative controls are important to the success of the two-photon microscopy experiment, which is used to measure motility of lymphocytes on the LN FRCn. The HIV negative control group will be

used to determine normal motility and samples obtained from HIV infected subjects on losartan and placebo will then be compared to these results. We have preliminary data from similar experiments conducted in mice to suggest that 10 control subjects will be adequate to establish normal motility.

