8.1.2 Baseline Visit

Designated study staff will review medical history with the participant and perform a targeted physical exam (vitals, heart, lung, abdomen, neurologic system). The subject will not be randomized until lab results have been reviewed and found to be within limits designated in the protocol. The designated study staff or principal investigator will sign off on lab results and eligibility criteria on the day of randomization to ensure labs are no more than 60 days old and the subject still meets all eligibility criteria. Blood will then be drawn for CBC, comprehensive metabolic panel (CMP – includes electrolytes, creatinine, and liver function tests), CD4 and VL as well as plasma, serum and PBMCs for study endpoints. Subjects in the two-photon microscopy sub-study will also have an additional 90cc of blood drawn. Inguinal LN biopsy and colonoscopy with ileal and rectal biopsies will be performed (described in detail in section 7.1 above). They will remain in the MCRU for 4 hours after procedures for monitoring.

Following procedures, subjects will be randomized to receive either losartan or placebo. The drug will be dispensed to the participant to begin administration on that day. At this baseline visit, participants will start losartan or matching placebo at 50mg daily. Prior to the first dose, the subject will be counseled regarding dosing schedule, potential side effects, and the importance of adherence. A member of the study team will contact the subject by telephone at day 7 to check for tolerability.

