8.4.2 MRI Sub-Study

Within two weeks of the biopsy a MRI will be scheduled, see Appendix I for MRI sub-study protocol.

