8.4.3 Study Visit(s)

If subject agrees to participate in the trial they will return to the MCRU to receive Stribild and Prezista. The subjects will take these medications for two weeks and return to be seen by the designated study staff. At this time a review of the medical history with the participant and a targeted physical exam will be performed. Blood will then be drawn for CD4, plasma, serum and PBMCs. Inguinal LN biopsy with colonoscopy with ileal and rectal biopsies will be performed. During this time blood draws will be taken at baseline and hours 1,2,3,4,6,8,12, and 24 post-drug administration. The subject will remain at the

MCRU for 12 hours for monitoring. They will then return to the MCRU the following morning for one additional blood draw at 24 hours after drug administration. They will complete the off-study form prior to discharge from the MRCU. Subjects will be instructed to report any subsequent event(s) within 3 months of study completion that the subject, or the subject's personal physician, believes might reasonably be related to participation in this study.

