8.5 Schedule of Events for Additional 5 Control HIV Uninfected Subjects

Table 2. Protocol summary for HIV uninfected (control) subjects:

	Screen	Study Drug Pick-Up	MRI	Week 2
Medical history	X			
Interval medical history				X
Physical Exam ¹	X			X
Safety screening			X	
MRI			X	
Adherence counseling		X		
Pregnancy test ²	X			
HIV & HCV Ab	X			
CMP	X			X
CBC w diff	X			X
CD4 count	X			X
Serum ³				X
Plasma /PBMCs ⁴				X
Biopsies ⁵				X
PK assessment ⁶				X

1. At screening, a full physical exam will be performed. At the Week 2 visit, a targeted exam will be performed.
2. Women of childbearing age must have a negative pregnancy test prior to enrollment.
3. Serum will be used to determine levels of IL-7 and TGF-beta.
4. Plasma will be used to determine levels of cytokines and markers of inflammation. PBMCs will be used in flow cytometry and intracellular cytokine staining. Additional blood will be obtained for two-photon microscopy.
5. Inguinal LN biopsy and colonoscopy with sampling of ileal and rectal tissues.
6. Intensive 24-hour PK assessment

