9.3 Recording and Documentation of AEs

At each contact with the subject, designated study staff must seek information as to discomforts or adverse experiences by specific questioning and, as appropriate, by examination. At study visits, safety laboratory evaluations will also be performed to identify any laboratory AEs. All side effects will be reported to the PI and/or physician co-investigators on a daily basis and toxicity laboratory results will be reviewed in real time. Information about AEs to be recorded includes event description, time of onset, investigator assessment of severity, relationship to study agent(s)/Intervention(s), and time of resolution/stabilization of the event. All AEs occurring during the study period (from time of consent signing to 3 months after the last study visit) must be documented appropriately regardless of relationship to study products or procedures. Information on all AEs will be promptly recorded in the source document and also in the appropriate AE module of the case report form (CRF).

Any medical condition that is present at the time that the participant is screened should be considered as baseline and not recorded as an AE. However, if the condition deteriorates at any time during the study it should be recorded and reported as an AE. Changes in the severity of an AE should be documented to allow an assessment of the duration of the event at each level of intensity to be performed. Adverse events characterized as intermittent require documentation of the onset and duration of each episode. Changes in the assessment of relationship to the study agent(s)/interventions should also be clearly documented.

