9.7.2 Stopping Rules for an Individual Participant

Subjects may withdraw from the study (and all follow-up procedures) for any reason and at any time. Participants may also choose to discontinue study medication and continue all follow-up procedures. This is most likely in the event of a toxicity that, in the opinion of the investigators, is related to the study agents.

If a subject withdraws, attempts will be made to schedule and conduct an early termination visit as described in section 8.1.11. The reason and date of withdrawal will be documented on the subject's CRF. Date of withdrawal will be documented as the date of last study drug treatment, not the date that the decision to withdraw was made. Participants will be followed after withdrawal from the study for 3 months after discontinuation. All AEs during that period will be reported.

The PIs may withdraw participants to protect their safety or if participants are unable or unwilling to comply with visits, study procedures, or study medication. Participants will be removed from the study if they experience any drug-associated toxicity > grade 2 and it is judged to be due to losartan (e.g., a complication of the biopsy procedure may not necessitate removal from the study). Subjects will not be withdrawn if they experience toxicity > grade 2 that is deemed due to Gardasil but will not continue to be given Gardasil. Subjects will also be removed in the event of pregnancy. Healthy controls will be removed from the study if they experience rash, moderate GI symptoms and/or symptoms consistent with clinical hepatitis with no other medically reasonable cause. Other exit criteria include:

- completion of the study,
- withdrawal of consent,
- moving to an area that would prohibit the subject from returning for visits, and
- death.

Even though subjects may be withdrawn prematurely from the study, we will continue to collect survival data on such subjects throughout duration of the 30 months. If a subject withdraws consent to participate in the study, attempts will be made to obtain permission to record survival data up to the 30-month end point. Methods used for follow up will include at least 5 phone calls and 3 letters to the participant.

Any subject withdrawn from the study prior to Month 1 will be replaced by another enrolled participant to meet study objectives.

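### The five HIV-uninfected volunteers on Stribild and Prezista have no fixed tolerability check before Week 2, and the >Grade 2 stopping rules do not name their drugs

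*Combined protocol and SAP*

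**What the plan says.** **Contacts.** Under 8.4.3 the five additional controls collect Stribild and Prezista, take them for two weeks and return. Table 2 has four columns: Screen, Study Drug Pick-Up, MRI and Week 2. Section 2.2 places the MRI within dosing: "This test will occur once during the two weeks while they are taking the antiretrovirals, prior to the biopsy". Section 8.4.2 fixes no day either: "Within two weeks of the biopsy a MRI will be scheduled". The Week 2 visit is still on drug: "During this time blood draws will be taken at baseline and hours 1,2,3,4,6,8,12, and 24 post-drug administration". It has an interval history, CMP and CBC, and the Table 2 footnote adds: "At the Week 2 visit, a targeted exam will be performed".

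For the losartan/placebo group, 8.1.2 provides an early check: "A member of the study team will contact the subject by telephone at day 7 to check for tolerability". Section 8.4 has no counterpart.

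**Stopping.** Controls have the removal rule in 9.7.2: "Healthy controls will be removed from the study if they experience rash, moderate GI symptoms and/or symptoms consistent with clinical hepatitis", unless there is another reasonable medical cause. Beyond that the section is permissive: "The PIs may withdraw participants to protect their safety". The mandatory rules for toxicity above Grade 2, in 9.6 and 9.7.2, name losartan and Gardasil only. Section 9.4.2 nevertheless lists darunavir and the Stribild combination as study agents for expedited reporting.

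**Entry.** The eight HIV-uninfected exclusions in 5.2 contain one laboratory limit, for AST/ALT. Creatinine is drawn at control screening (8.4.1) with no cut-off attached. HIV-infected subjects have an eGFR exclusion (item 8). Section 2.4.1 names renal impairment as a Stribild risk.

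**The concern.** These volunteers have no therapeutic need for either product and, under 2.4.2, no direct benefit. The main protection written for them is a rule triggered by symptoms, and such a rule works only if someone hears about the symptom while there is still dosing to stop. Week 2 closes the course, so a rash or moderate GI upset first elicited there is found too late for removal to spare much exposure. Before that, detection depends on one imaging visit of unknown timing and on the volunteer calling in.

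The second exposure is a severe reaction outside the three listed symptom groups. The same grade of reaction ends losartan or Gardasil dosing by rule. For Stribild or Prezista the decision is left to judgement.

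**Working it through.** The plan gives no figure to reproduce. The check is a count of contact intervals and a side-by-side reading of the rules.

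**Contact interval**

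Inputs: two weeks of dosing (2.2, 8.4.3), one MRI during dosing and before the biopsy (2.2), and a Week 2 visit that includes the biopsy (8.4.3, Table 2).

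Assumptions: first dose on the pick-up day (day 0), Week 2 at day 14, MRI on day *m* with *m* from 1 to 13. The documents do not state *m*.

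Longest interval without a scheduled contact = max(*m*, 14 − *m*).

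| MRI day *m* | Longest gap (days) | Longest gap with a day-7 call |
|---|---|---|
| 1 or 13 | 13 | 7 |
| 2 or 12 | 12 | 7 |
| 3 or 11 | 11 | 7 |
| 4 or 10 | 10 | 7 |
| 5 or 9 | 9 | 7 |
| 6 or 8 | 8 | 7 |
| 7 | 7 | 7 |

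The range is 7 to 13 days, and the gap exceeds 7 days unless the MRI falls exactly on day 7. A call at day 7 divides the course into two halves of 7 days. The MRI can split at most one half, so the longest gap becomes 7 days for every *m*.

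**Stopping rules**

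| Reaction judged due to | Mandatory stop above Grade 2 (9.6, 9.7.2) | Other mandatory stop |
|---|---|---|
| Losartan | Yes | – |
| Gardasil | Yes, further doses withheld | – |
| Stribild or Prezista | None written | Controls: rash, moderate GI symptoms, hepatitis symptoms |

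Comparing the control rule with the risks listed in 2.4.1:
- Covered: rash and skin reactions, nausea, diarrhea, vomiting, abdominal pain, hepatitis and jaundice. For rash (no grade floor) and GI symptoms (moderate), the rule acts below Grade 3.
- Not covered: headache, dizziness, insomnia, fatigue, renal impairment and hyperglycemia. An ALT rise without symptoms is also outside the rule.

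The grade 3 stop in 8.1.3 does not fill this gap. It sits in the HIV-infected schedule and is written around the 50 mg and 100 mg losartan/placebo doses.

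**Laboratory timing**

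Table 2 lists CMP at Screen and Week 2 only. The losartan/placebo group also has its first scheduled on-drug CMP at day 14 (8.1.3, Table 1). The two groups are therefore alike on laboratory timing and differ on the day-7 call.

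**Renal entry**

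None of the 8 HIV-uninfected exclusions is renal. The staff check of laboratory eligibility in 8.4.1 therefore has no creatinine criterion to apply.

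**The case against.** The strongest reply is that existing safeguards already cover most of this. The control rule is mandatory and matches many of the reactions listed in 2.4.1. The MRI visit includes an Appendix I interview about general health, medications and conditions including fever. Section 9.3 adds: "At each contact with the subject, designated study staff must seek information as to discomforts or adverse experiences by specific questioning". Section 9.3 also requires side effects to go to the study physicians daily, 10.1 tells subjects to report adverse events at once, 7.2 promises renal and liver monitoring, and 6.3 requires package-insert review when a study agent is started. All of this stands and lowers the severity. None of it creates a dated contact before Week 2 other than the MRI, or a mandatory stop for the uncovered reactions.

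A second reply is that the extended stop would have little to act on. That is partly right. No laboratory result is scheduled between pick-up and Week 2, and a phone call cannot detect a silent creatinine rise. The rule would act on reported events and unscheduled results only.

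A reader might also infer more than the documents support:
- *That controls have no mandatory stop.* They have one, and for rash and GI symptoms it is stricter than the losartan rule.
- *That controls get later laboratory checks than losartan subjects.* First on-drug chemistry is at day 14 in both groups.
- *That a typical gap can be stated.* An average would need a distribution of MRI days, and none is given. Only the range is supported.
- *That an early stop costs 1 of 5 (20%) of this group's PK profiles.* Section 9.7.2 requires replacement of any subject withdrawn before Month 1. Read literally, that includes a two-week volunteer.
- *That renal risk is unguarded at entry.* Investigator discretion, the ban on nephrotoxic drugs (6.4) and package-insert review give partial cover. What is missing is a written limit.

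**Conclusion.** The point holds as a participant-safety improvement of modest size. Five volunteers on a 14-day course have a longest gap of 7 to 13 days without a scheduled contact, depending on the MRI day. Severe reactions outside rash, GI and hepatitis symptoms have no mandatory stop for the two drugs they take. The gap range assumes dosing starts at pick-up, Week 2 falls on day 14 and the MRI is on days 1 to 13. It measures scheduled contact, not harm: the documents give no event rate for two weeks of these drugs in healthy people, so the expected benefit of the change is not quantified.

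The missing renal limit is real but secondary. The volunteers are non-randomized and contribute to exploratory endpoints, so the losartan versus placebo comparison is unaffected.

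**What to change.** 1. **Day-7 call.** Add the telephone tolerability call of 8.1.2 to 8.4 and as a column in Table 2. This caps the gap at 7 days wherever the MRI falls and lets the existing symptom rule act mid-course.
2. **Stopping rule.** In 9.6 and 9.7.2, extend mandatory discontinuation for drug-related toxicity above Grade 2 to Stribild and Prezista. Keep the stricter control rule alongside it, and state that before Week 2 the new rule acts on reported events and unscheduled laboratory results.
3. **Secondary.** In 5.2, add a renal limit for volunteers who will take Stribild, applied to the creatinine already drawn at screening. Take the threshold from the current package insert that 6.3 requires investigators to review. The documents give no figure, so none is proposed here.

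Cost: five calls by existing staff, a short amendment and no new blood test. There may be a screen failure or an early stop. It would help to confirm in 9.7.2 that the replacement rule covers these controls, since its Month 1 limit refers to a visit that only the HIV-infected schedule contains.

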9.8 Unblinding Procedures

The Investigational Drug Service (IDS) Pharmacy is responsible for the administration of the blinded study agent as the intervention. This pharmacy holds the record of randomization for this study. The study participant, investigators, study coordinator, other study staff, statistician, and DSMB are blinded. The following conditions or events in which unblinding may occur are:

9.8.1 Emergency Unblinding

Please see Fairview IDS Pharmacy Emergency Blind SOP for detailed description of the unblinding process that will occur in the case of an emergency.

9.8.2 Individual Unblinding

For individual unblinding, the PI should assess the need for unblinding where a SAE has occurred and the treatment or allocation code is required in order to enable clinical treatments to be planned. In the event that this occurs, the IDS pharmacy will be contacted by a member of the study staff and given the following details: caller name and position, study site, site investigator, name of participant, study protocol number, and subject identification number. Upon unblinding, the study staff member will record the participant withdrawal and allocation in the person's clinical and trial notes along with appropriate clinical notations. The study staff member will log the unblinded reports and the PI will report unblind rates to the local IRBs, DSMB, OHRP, and DAIDS.

9.8.3 Unmasked Analysis

The DSMB will determine that an unmasked analysis is required. The decision will be documented in the committee meeting minutes. A DSMB designee will make a written request to the PI for study unblinding. The PI will request the IDS pharmacy to provide randomization schedules to the DSMB designee. The IDS pharmacy will check the allocation log for completions to date, sign and date the last entry with a note to indicate point of request, and provide the DSMB designee with the register of all study allocations. The lead statistician will merge the study data with the table of allocation codes as per the data transfer instructions within the data management plan and undertake unmasked analysis as determined by the DSMB.

9.8.4 Unblinding Upon Study Completion

The PI will determine that study recruitment is complete and unblinding is required for analysis. A study staff member will contact the IDS pharmacy for the schedules and a request for return all unblinded study agent. The IDS pharmacy will check the allocation log for completion, sign and date the last entry, provide the study staff member with the schedule of all study allocations, and ensure all invoicing has been completed. The study staff member will enter all identification numbers and allocations into a file and send the file to the statistician as outlined in the Data Management Plan. The statistician will confirm receipt of the file containing the ID numbers and allocations, and merge the study data with the new file in preparation for analysis.

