4. STUDY DESIGN

4.1 Description of the Study Design:

This is a randomized, double-blind, placebo-controlled trial of 50 HIV-1 infected individuals on stable ART randomized in a 1:1 ratio to losartan (50 mg orally daily titrated to 100 mg daily) vs placebo for 30 months. We plan to enroll a total of 63 HIV infected subjects to ensure that 50 complete the protocol. All HIV infected subjects will undergo biopsies of inguinal lymph node (LN) and gut associated lymphatic tissue (GALT) for primary endpoint analysis at baseline, 12 and 30 months after study enrollment. Blood will be collected at least quarterly throughout the study and an intensive blood pharmacokinetic (PK) study will be conducted at month 1. All HIV infected subjects will be vaccinated with the quadrivalent human papillomavirus (HPV) vaccine at months 23, 25 and 29.5. 5 HIV uninfected control subjects will also be enrolled. They will not receive study agents or HPV vaccination and will undergo blood draw and inguinal LN biopsy at one time point only. We anticipate completing subject enrollment over a 14 month period and plan to complete all subject follow up 44 months after the first subject is enrolled.

4.2 Study Endpoints:

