11.3 Enrollment/Stratification/Randomization/Blinding Procedures

HIV infected subjects will be randomized to receive losartan or placebo in a 1:1 manner using ordinary methods for generating random deviates. Study staff (other than those in the IDS pharmacy) and participants will be blinded to the random assignments of all HIV infected study participants. All study drug will be supplied in identical containers.

The two-photon microscopy sub-study of the HIV infected subjects requires 5 participants on losartan and 5 on placebo. Investigators are blinded to treatment assignment. To be able to ensure we have the 5 on losartan and 5 on placebo we will give the list of all subjects who agree to the sub-study to the investigation pharmacist who maintains the blind. They will identify the ten participants we should use for the sub-study.

Blinding will be maintained until all data are entered into the study database, all study endpoint data and other data included in the final analysis have been verified and the data are ready for final analysis. This will be explained to participants as part of the study. Unblinding will occur according to standard operating procedures as per section 9.13.

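### Section 9.8.4 ties end-of-study unblinding to completed recruitment, which conflicts with section 11.3 and, read literally, permits release of allocations up to 30 months before the last primary-endpoint biopsy

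*Combined protocol and SAP*

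**What the plan says.** Section 9.8.4 is headed "Unblinding Upon Study Completion". Its first sentence reads "The PI will determine that study recruitment is complete and unblinding is required for analysis". A study staff member then asks the pharmacy for the allocations, and the pharmacy is to "provide the study staff member with the schedule of all study allocations". Next, "The study staff member will enter all identification numbers and allocations into a file", and the file goes to the statistician, who merges it with the study data.

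Section 11.3 states a different condition: "Blinding will be maintained until all data are entered into the study database", and until the endpoint and other final-analysis data "have been verified and the data are ready for final analysis". It closes with "Unblinding will occur according to standard operating procedures as per section 9.13". Section 9 ends at 9.8, so that reference leads nowhere.

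Section 9.8 lists the participant, investigators, coordinator, other study staff, statistician and DSMB as blinded. Section 11.5 places the final analysis after all the data are available.

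On timing, section 4.1 expects accrual to take 14 months and the last follow-up to end at month 44, counted from the first enrolment. It puts the biopsies for the primary endpoint at baseline, month 12 and month 30.

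**The concern.** The protocol gives two milestones for the same event. One is the end of recruitment plus a judgement by the PI that unblinding is needed for analysis. The other is a complete, verified data set. The cross-reference that should join them is broken, and 9.8.4 is the only section that sets out the end-of-study steps. A coordinator or pharmacist looking for the procedure would therefore find the weaker condition.

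If 9.8.4 were followed to the letter, a member of the study staff could hold every allocation during follow-up. In that period the protocol still leaves matters to judgement: dose changes and re-challenge (8.1.3), attribution of adverse events (9.3.2), withdrawal by the investigators (9.7.2), and laboratory decisions to reject data (14.3). If knowledge of allocation spread, it could affect retention, safety attribution and the handling of the month-30 tissue.

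**Working it through.** **Inputs.** Accrual 14 months and end of all follow-up at month 44 (4.1). Follow-up of 30 months per HIV-infected participant (Protocol Summary). Biopsies at baseline, month 12 and month 30 (2.2, 4.1). First HPV vaccination at month 23 (4.1). Planned enrolment 63, so that 50 complete (2.2, 4.1).

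**1. The plan's own figure.** Accrual + follow-up = 14 + 30 = 44 months. This matches the stated 44.

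**2. Gap between the milestones.** The last month-30 biopsy falls at month 44. Recruitment ends at month 14. Gap = 44 − 14 = 30 months. The gap does not depend on the accrual period: with accrual of 15, 18 or 24 months the last biopsy moves to month 45, 48 or 54, and the difference is still 30.

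**3. What would be in hand at month 14.**
- Month-30 biopsies: none. The first participant's is due at calendar month 30, which is 30 − 14 = 16 months later.
- HPV vaccinations: none. The first is due at calendar month 23, which is 23 − 14 = 9 months later.
- Month-12 biopsies: only participants enrolled in the first 14 − 12 = 2 months are due. The documents give no accrual curve. If accrual is uniform (assumption), the share is 2/14 = 14.3%, and 63 × 2/14 = 9 participants before any drop-out.

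**4. Sensitivity to slower accrual** (uniform accrual over A months; share past month 12 when recruitment closes = (A − 12)/A):

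| A (months) | Share past month 12 | Of 63 | Past month 30 |
|---|---|---|---|
| 14 | 2/14 = 14% | 9 | 0 |
| 18 | 6/18 = 33% | 21 | 0 |
| 24 | 12/24 = 50% | about 32 | 0 |

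The month-12 count depends on the assumed accrual. The absence of month-30 tissue does not, for any accrual period shorter than 30 months.

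**5. The two rules side by side.**

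| | 9.8.4 | 11.3 |
|---|---|---|
| Milestone | Recruitment complete | All data entered |
| Further condition | PI judges unblinding is needed for analysis | Endpoint and final-analysis data verified and ready |
| Follow-up finished? | Not stated | Implied by all data entered |
| Earliest planned date | Month 14 | Not before month 44 |
| Who receives the schedule | Study staff member, then statistician | Not stated; refers to 9.13 |

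**The case against.** The strongest reply is that 9.8.4 has two conditions, not one. Unblinding must also be required for analysis, and under 11.5 the final analysis waits for all the data. An unmasked analysis during the trial has its own route through the DSMB in 9.8.3. The heading refers to study completion. The other steps, such as return of study agent and settled invoices, describe a close-out and do not fit month 14, when participants are still being dosed. Section 11.3 is also operative text and already holds almost all of the needed safeguard. The 9.13 reference looks like stale numbering: section 8.1.12 likewise sends the reader to a non-existent 9.9 for pregnancy.

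Most of this stands. It shows that recruitment is probably a slip and that the trial does not plan to unblind at month 14. It does not make the sentence safe. The second condition is left to the PI and does not say which analysis is meant, and the month-12 biopsies are themselves taken for the primary endpoint. A heading does not override the sentence beneath it. The data management plan and the standard operating procedures may say more, but they are not among the documents.

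Three stronger readings are tempting, and the documents do not support them:
- A reader might infer that the PI would hold every allocation. Section 9.8.4 names only a study staff member and the statistician as recipients.
- A reader might infer that the trial would become open-label. Nothing in 9.8.4 reveals assignments to participants.
- A reader might turn the gap into a share of unblinded person-time: with mean follow-up of 14/2 = 7 months at the trigger, (30 − 7)/30 = 77%. That figure describes a course that 11.3 forbids, and it ignores the 20–25% drop-out expected in 2.2. It does not measure an expected effect.

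**Conclusion.** The point holds as an internal inconsistency in an operative blinding rule. It is not a criticism of a design choice. Section 9.8.4 is wrong as written: it names completed recruitment, with the PI's judgement that unblinding is needed for analysis, where 11.3 requires complete and verified data. The wording permits, though the trial probably does not intend, release of the full allocation schedule to a study staff member up to 30 months before the last primary-endpoint biopsy.

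The 30-month gap follows from the 30-month follow-up alone and needs no assumption about accrual. The count of about 9 of 63 past month 12 assumes uniform accrual over the planned 14 months and no drop-out. Sample size, power and significance level are unaffected.

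**What to change.** 1. In 9.8.4, replace completion of recruitment as the trigger with the 11.3 condition: the last participant's month-30 visit is done, all endpoint data are entered and verified, and the database is locked. Lock is an addition to 11.3; it turns readiness for analysis into a dated event.
2. In 11.3, change the reference from section 9.13 to section 9.8. The whole of 9.8 is the right target because it also covers emergency, individual and DSMB unblinding.
3. Optional: have the pharmacy send the allocation file directly to the statistician. This removes a manual re-keying step for which 9.8.4 describes no check. Once the database is locked, the present route carries little risk to the blind, so this matters less than the first two changes.

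The cost is wording in two sections. No participants, visits or assays are added.
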